#### 17.2 Trial questionnaires

Participants will be sent a link to complete their trial questionnaires electronically where possible. Any link to a questionnaire sent to a participant either by email or text is unique to a participant and their time point/questionnaire in the trial. For those participants indicating that they will be unable to complete questionnaires electronically, data will be collected through telephone interview or via postal questionnaire. Where paper-based questionnaires are used, data will be entered into the trial database by the central trial team.

Clear guidance will be provided about how to complete each part of the questionnaire. If the participant does not complete the follow-up questionnaires, they will receive a reminder email, text and/or postal reminder, followed by one or more phone calls by the central trial team to offer assistance in the completion of the questionnaires or to complete the questionnaires over the phone. This will reduce drop out. The follow-up strategy will be described in the Data Management Plan. The central trial office may also phone participants to resolve data queries.

Table 4: Schedule of assessments

Assessments	≤21 days	3, 5	2	11, 14	4	20, 23	6
	post-injury	wks	mnths	wks	mnths	wks	mnths
Confirmation of eligibility	Х						
Informed Consent							

Injury details and medical history	Х						
Oxford Shoulder Score	Pre-injury		Х		Х		Х
(OSS)	and						
	Post-injury						
	Baseline						
PROMIS Physical Function	Baseline		Х		Х		Х
(Upper Extremity)							
Self-efficacy (confidence)	Baseline		Х		Х		Х
to Exercise (SEE)							
Health-related quality of	Pre-injury		Х		Х		Х
life (EQ-5D-5L)	and						
	Post-injury						
	Baseline						
Complications			Х		Х		X*
Resource use			Х		Х		Х
questionnaire							
Exercise information			X		Х		Х
Physio attendance (usual		Х	Х	Х	Х	Х	Х
care group only)							
Further physio delivery							Х
information (pilot phase –							
where physiotherapy is							
provided by the recruiting							
NHS Trust)							

Retrospective pre-injury baseline OSS and EQ-5D-5L will be collected at time of consent.

## 17.3 Data Collection

Data will be collected as described at each of the time points defined below.

## 17.3.1 Baseline

Baseline data will be collected prior to randomisation, with the exception of physiotherapy referral information, which will be post-randomisation.

Data sourced/collected by local research team	Data directly reported by participants

 
Participant demographics
 
Injury details and medical history
 
Physiotherapy referral information (usual care group only): date and location (recruiting trust or community)
 
	
 
OSS questionnaire – pre-injury and post-injury baseline
 
PROMIS Upper Extremity questionnaire – baseline
 
EQ-5D-5L questionnaire – pre-injury and post-injury baseline
 
SEE questionnaire – baseline
 

# 17.3.2 Follow-up assessments/subsequent visits

## 3 & 5 weeks post-randomisation (usual care only)

\*Additional site reported questionnaire

Data sourced/collected by local research team	Data directly reported by participants
n/a	Physiotherapy appointments attended

# 2 months post-randomisation

Data sourced/collected by local research team	Data directly reported by participants (patient-reported outcomes)
Ad hoc – Serious Adverse Event (SAE) CRF	OSS questionnaire
completion, Death notification	PROMIS Upper Extremity questionnaire
	SEE Scale questionnaire
	EQ-5D-5L questionnaire
	Resource use questionnaire
	Complications and exercise information
	questionnaire
	Physiotherapy attendance

# 11 & 14 weeks post-randomisation (usual care only)

Data sourced/collected by local research team	Data directly reported by participants
n/a	Physiotherapy appointments attended

# 4 months post-randomisation

Data sourced/collected by site research team	Data directly reported by participants (patient-reported outcomes)
Ad hoc – SAE CRF completion, Death notification	OSS questionnaire
	PROMIS Upper Extremity questionnaire
	SEE Scale questionnaire
	EQ-5D-5L questionnaire
	Resource use questionnaire
	Complications and exercise information questionnaire
	Physiotherapy attendance

# 20 & 23 weeks post-randomisation (usual care only)

Data sourced/collected by local research team	Data directly reported by participants
n/a	Physiotherapy appointments attended

# 6 months post-randomisation

Data sourced/collected by site research team	Data directly reported by participants (patient-
	reported outcomes)

Complications (Medical Notes)	OSS questionnaire
Further physio delivery information (pilot	
 
PROMIS Upper Extremity questionnaire
 

phase – where physiotherapy is provided by	SEE Scale questionnaire
the recruiting NHS Trust)	EQ-5D-5L questionnaire
	Resource use questionnaire
Ad hoc – SAE CRF completion, Death notification	• Complications and exercise information
	questionnaire
	
 
Physiotherapy attendance
 

#### 17.4 Qualitative assessments

No qualitative research is currently planned as part of the trial.

#### 17.5 Withdrawal

Withdrawal of consent means that a participant has expressed a wish to withdraw from the trial altogether or from certain aspects of the trial only. The type of withdrawal will be collected on the CRF labelled 'Withdrawal'.

The Withdrawal CRF should be completed to document the reasons for withdrawal, if provided, the level of withdrawal and who the decision to withdraw was made by.

Where a participant expresses a wish to withdraw from the trial, the research team will record the level of withdrawal – a) no longer willing to complete trial questionnaires (data will still be collected for study purposes) or b) full withdrawal (data collection will stop).

Participants may also be withdrawn from the trial (or aspects of the trial) by their clinician if they believe the participant needs to be withdrawn to safeguard the safety or wellbeing of the participant.

A decision to no longer adhere to the trial procedures by either participants or clinician (i.e. not attend scheduled physiotherapy sessions, no interaction with the provided materials, referral to physiotherapy, later surgery or other complications) will not be considered a trial withdrawal.

The site research team can request withdrawal of a participant by email to the central trial team. Appropriate action will be taken by the trial teams (centrally and by the local research team at each participating site) to ensure compliance with the participant's withdrawal request. This may include marking future CRFs as not applicable and ensuring any relevant communications which the participant had consented to receive regarding their participation are no longer sent.

Data collected up to the point of withdrawal will be used and analysed as explained in the PIS. Investigators should continue to follow-up any ongoing SAEs to resolution in the CRF in accordance with the safety reporting section.

Withdrawn participants will not be replaced.

#### 18 BLINDING AND CODE BREAKING

#### 18.1 Blinding

It is not possible to blind trial participants or those delivering the interventions. Those involved in the care of participants or delivery of the interventions will not be involved in outcome data collection or analysis. The outcome data will be collected directly from the participants. Table 5

provides an overview of the blinding status of all individuals involved in the conduct and management of the trial.

Table 5: Blinding status of those involved in trial conduct and management.

Role in trial	Blinding status	Additional information
Participants	Not blinded	Not possible due to the nature of the intervention.
Site research staff including PI	Not blinded	Not possible due to the nature of the intervention.
CI	Blinded for	It is not possible to blind the CI as they may be the
	those at sites	primary clinician for those participants recruited at their
	other than their	site, however, they will be blinded to allocations for
	own, except for	participants at other sites. In instances where SAEs are reported,
	any SAE	the CI will become unblinded to complete the full causality
	causality	assessment.
	assessment	
Database	Not blinded	The database programmer is responsible for the management of
programmer		the REDCap database and will have access to all unblinded
		datasets.
Central trial team	Not blinded	Members of the central trial team will not be blinded to
		treatment allocations as site staff may require support for
		randomisation, or participants may contact the trial team
		directly. SAE reports will also be handled by the trial
		management team which will contain allocation information.
		Staff calling participants to collect outcome data will receive
		training and follow scripts to ensure a consistent approach.
Data Management	Not blinded	Data management staff will have access to the unblinded
		datasets within the trial randomisation system and database to
		ensure data quality and undertake central monitoring activities.
Trial Statistician	Not blinded	The trial statistician and senior trial statisticians will have access
and Senior Trial		to treatment allocations or data needed for generating the Data
Statistician		and Safety Monitoring Committee (DSMC) closed reports and the
		final analysis and will remain blinded while performing any data
		cleaning.
Health Economist	Not blinded	The trial health economist and senior health economist will have
		access to treatment allocations for the final analysis.

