#### 15.2 Randomisation procedure

Eligibility will be reconfirmed at randomisation. Participants will be randomised using the REDCap Randomisation Module provided within the core code of the REDCap application. This module has been validated for use by OCTRU and is accessed via the REACH REDCap trial database.

Participants will be randomised to one of the following two treatment groups:

Table 3: Treatment groups

Group	Description
Self-directed rehabilitation (intervention)	Detailed advice from a trained health professional and a workbook and website with a set of exercises that can be progressed independently.
Physiotherapist-supervised rehabilitation as per usual care (control)	Usual fracture clinic advice and referral to physiotherapy

Upon randomisation of a participant the central trial team and a member of the site research team will be notified by an automated email. Patients who are being consented using the remote consent method will be called by the site research team following randomisation and informed of their allocation.

Full details of the randomisation procedure will be stored in the Randomisation and Blinding Plan in the confidential statistical section of the TMF.

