## 23.2 Sample Size/Power calculations

The primary outcome measure is the OSS at 6 months post-randomisation. Previous studies have demonstrated a minimum clinically important difference (MCID) of 5 points and a standard deviation of 12 (1). One method for choosing the non-inferiority margin is to take half the MCID and this is the method used in this trial. In real terms, a 2.5 point worse score equates to dropping one level on more than two of the twelve questions e.g. moving from little to moderate difficulty in more than two functional tasks such as household shopping and hanging clothes in a wardrobe. To ensure the acceptability of this margin with patients and clinicians we undertook consultations with stakeholder representatives. A 5% worse outcome overall (2.5/48) would be acceptable to avoid the burden of multiple outpatient visits and is sufficient to change clinical decision making. Primary outcome data provided by 970 participants at 6 months will provide 90% power at 2.5% (1-sided) significance to detect whether self-directed rehabilitation is non-inferior to standard physiotherapist-supervised rehabilitation based on a non-inferiority margin of 2.5. Allowing 20% loss to follow-up yields an overall sample size of 1214 (607 per group).

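### Some 6-month OSS scores may be taken by telephone by central staff who know the allocation, although none of the stated reasons for unblinding requires it

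*Protocol*

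**What the plan says.** Protocol section 23.2 fixes the deciding variable: "The primary outcome measure is the OSS at 6 months post-randomisation". Section 9.6 describes it as 12 patient-reported items, each with five response levels, totalling 0 to 48.

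Section 10.2 makes follow-up mainly electronic, with telephone or post as options. Section 17.2 gives the detail. For participants who cannot use electronic forms, "data will be collected through telephone interview or via postal questionnaire". Non-responders first receive reminders by email, text or post, "followed by one or more phone calls by the central trial team to offer assistance in the completion of the questionnaires", and the form may be completed during the call. Section 17.2 adds: "The central trial office may also phone participants to resolve data queries".

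On knowledge of the allocation, section 15.2 says: "Upon randomisation of a participant the central trial team and a member of the site research team will be notified by an automated email". Table 5 in section 18.1 classes the central trial team as not blinded: "Members of the central trial team will not be blinded to" treatment allocations. It gives three reasons: sites may need help with randomisation, participants may contact the team, and SAE reports show the arm. The same row covers the staff who phone participants for outcomes and gives them training and scripts. The text above the table offers a further safeguard: "Those involved in the care of participants or delivery of the interventions will not be involved in outcome data collection or analysis".

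**The concern.** The OSS is a subjective score of pain and function, and the trial is decided by where the lower confidence limit falls relative to -2.5. A caller who knows the arm and is helping someone choose between adjacent response levels can influence the answer, even without intending to. Scripts standardise the wording but do not hide the arm.

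The exposure is hard to justify by need, because each reason in Table 5 concerns a different task from an outbound outcome call. The protocol separates knowledge of the allocation in other roles: the chief investigator is blinded for other sites, and the statisticians stay blinded while cleaning data. Section 25.6 limits data access by role, and section 25.7 mentions access controls within the application.

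The forms themselves can also reveal the arm. Table 4 marks physiotherapy attendance as usual care only, and it falls due with the OSS at 2, 4 and 6 months.

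If callers were more lenient towards self-directed participants, non-inferiority could be declared too readily. The reverse would cost power. The people reached by phone (late responders and some offline participants) are unlikely to be a random subset.

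**Working it through.** **Inputs from section 23.2:** margin 2.5, SD 12, one-sided 2.5%, power 90%, 970 analysed, 20% loss, 1214 randomised. Allocation is 1:1 (section 15.3).

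**Step 1. Reproduce the plan's figure.** n per arm = 2 × 12² × (1.960 + 1.282)² / 2.5² = 288 × 10.51 / 6.25 = 484.2, so 485 per arm and 970 in total. 970 / 0.8 = 1212.5, which is 607 per arm or 1214 with equal arms. This agrees with the protocol: "Primary outcome data provided by 970 participants at 6 months will provide 90% power at 2.5% (1-sided) significance".

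**Step 2. Standard error.** SE = 12 × √(2/485) = 0.771. The power check is Φ(2.5/0.771 − 1.960) = 90.0%.

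**Step 3. Effect of a differential interviewer effect.** Let p be the share of 6-month OSS scores taken by phone, the same in both arms. Let d be the between-arm difference in interviewer effect per phoned score. The estimated treatment difference then shifts by p × d. The SE is taken as unchanged.

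- False non-inferiority at a true difference of -2.5, bias favouring self-directed care: Φ(p·d/SE − 1.960)
- Power at a true difference of 0, bias against self-directed care: Φ((2.5 − p·d)/SE − 1.960)

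The protocol gives neither p nor d. The values below are assumptions.

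| p | d (points) | Shift p·d | False non-inferiority | Power, opposite bias |
|---|---|---|---|---|
| 0 | – | 0 | 2.5% | 90.0% |
| 10% | 0.5 | 0.05 | 2.9% | 88.9% |
| 10% | 1 | 0.1 | 3.4% | 87.6% |
| 20% | 1 | 0.2 | 4.5% | 84.7% |
| 20% | 2 | 0.4 | 7.5% | 77.8% |

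For the row at 10% and 0.5 point: 0.05/0.771 = 0.065 and Φ(0.065 − 1.960) = 2.9%; 2.45/0.771 = 3.179 and Φ(3.179 − 1.960) = 88.9%.

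**Step 4. Set the reasons against the task.** Randomisation support takes place at entry. Inbound contact is started by the participant. SAE reports come from sites through the database. None of these is the outbound 6-month OSS call, and none needs the allocation to be visible during it.

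**The case against.** The arrangement is disclosed and mitigated. Table 5 names training and scripts for callers in the same cell that leaves the team unblinded, so this is a design choice and not a contradiction. That stands: the point is that a better arrangement is available at little cost.

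The exposed share may be small. Follow-up is mainly electronic, calls to non-responders come only after other reminders, and sections 17.2 and 30.1 offer post to people with less IT access. A reader might infer that every offline participant is interviewed by phone by unblinded staff. The protocol does not say so. Post is an alternative, and the sentence on telephone interviews does not name who conducts them. Section 25.7, where central staff enter data captured on calls, makes the central team the natural reading, but this is an inference.

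Masking callers has limited benefit. Participants know their arm and score the items themselves, so their own reporting bias remains, and some will tell the caller their group. This stands. It limits the gain but is no reason to accept the additional interviewer effect.

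Fully separate callers could be awkward. If the OSS caller could never open the attendance form, usual-care participants completing by phone would need a second caller or call, in one arm only. This is a fair criticism of a strict separation, and the fix avoids it by ordering the call.

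Two further readings go too far. One is that query calls change submitted OSS answers: nothing in the protocol says so, and section 25.7 describes audit trails. The other is that section 18.1 misrepresents complications because it describes outcome data as coming straight from participants. Table 2 and sections 9.7.4 and 17.1 state the medical-record source plainly, so this is a clerical matter of wording and does not bear on the OSS.

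**Conclusion.** The point holds as a worthwhile improvement. Some 6-month OSS scores may be taken by callers classed as unblinded, with training and scripts as the only safeguard on the call, and no stated reason requires these callers to know the arm. Blinding status is set in this protocol, so it should be changed here even though section 17.2 leaves the follow-up strategy to the Data Management Plan.

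The size is unknown. On the assumptions shown, the effect on false non-inferiority runs from slight (2.9%) to material (7.5%), with matching losses of power if the bias runs the other way. A reader might take these figures as the trial's actual error rate. They are not: phone share, bias size and bias direction are all assumed, and with no differential effect the 2.5% is unaffected. The calculation also assumes equal phone shares in the two arms. If the shares differ, even an interviewer effect that is the same in both arms would shift the estimate, which is why mode should be reported by arm.

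**What to change.** In section 17.2 and Table 5, state the following.

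- Outbound OSS calls are made, wherever the existing team allows, by members whose REDCap role hides the allocation and who do not receive the allocation email described in section 15.2.
- The OSS is asked first, read verbatim, and saved before the usual-care-only attendance form or any physiotherapy or resource-use item is opened. The same caller can then finish the call.
- The caller records the mode of completion and whether the allocation became known before the OSS was saved. Both are reported by arm.
- A sensitivity analysis of the OSS by mode of completion is added. Mode is determined after randomisation, so this tests robustness and should not be read as a subgroup effect.

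The cost is a REDCap user role in line with the role-based access in section 25.6, a reordered script, two data fields and some wording. The downside is a small rota constraint, and some callers will still learn the allocation. The fix adds no visits, and limiting it to what the existing team allows means it does not depend on extra staff.

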# 18.2 Code break/ unblinding

Not applicable for this trial.

## 19 SAMPLES

This trial Protocol does not involve any taking of new biological samples or any use of pre-existing samples.

## 20 IMAGES

This trial protocol does not involve any taking of new images.

## 21 SAFETY REPORTING

## 21.1 Safety reporting period

Safety reporting for each participant will begin from randomisation and will end when the participant has reached their final follow-up time point, at 6 months post-randomisation.

#### 21.2 Definitions

Table 6: Definitions of adverse events

Adverse event (AE)	Any untoward occurrence in a clinical trial participant.  Note: An AE can therefore be any unfavourable and unintended sign (including an abnormal laboratory finding, for example), symptom or disease temporarily associated with the trial procedures, whether or not				
	considered related to the procedures.				
Related AE	An event that resulted from administration of any of the research procedures.				
SAE	An AE that:     results in death     is life-threatening  requires hospitalisation or prolongation of existing hospitalisation     results in persistent or significant disability or incapacity     is a congenital anomaly or birth defect; or     is otherwise considered medically significant by the Investigator  .				
Unexpected Related Serious Adverse Event	An SAE related to the trial (i.e. resulted from administration of any of the research procedures) and is unexpected (not listed in the Protocol as an expected occurrence).				

<sup>1 participant was at risk of death at the time of the event; it does not refer to an event which hypothetically might have caused death if it were more severe

A distinction is drawn between serious and severe AEs. Severity is a measure of intensity whereas seriousness is defined using the criteria above. Hence, a severe AE need not necessarily be serious.

#### 21.3 Foreseeable AEs

For this trial, foreseeable AEs will be recorded by participants or site staff but will not need to be reported immediately. These will be recorded on participant and site-reported CRFs up to 6 months post-randomisation. The foreseeable AEs for this trial have been identified as:

- increase in pain after shoulder exercises lasting more than one week and requiring initiation of pain medication or increase in pain medication or consultation with medical doctor
- diagnosis of Complex Regional Pain Syndrome
- diagnosis of venous thrombosis
- diagnosis of pulmonary embolism
- diagnosis of a post-traumatic neurovascular injury (including neuropathy/nerve palsy)
- diagnosis of post-traumatic (secondary) frozen shoulder (arthrofibrosis)
- surgery to the injured shoulder

<sup>2 Medical events that may jeopardise the participant or may require an intervention to prevent one of the above characteristics/consequences.

## 21.4 Non-reportable SAEs/AEs

AEs that are unrelated to the intervention will not be reported. AEs deemed related to the intervention that do not meet the SAE definition and are not classed as foreseeable as per section 21.3, will also not be reported.

## 21.5 Reporting of SAEs from sites to the central trial team

Only those adverse events that meet the definition of SAEs, are not listed as foreseeable AEs, and are considered by the site investigator to be related (possibly, probably, or definitely, see Table 7) to the trial intervention or any of the research procedures will be reported immediately to the central trial team as follows:

SAEs will be reported by the site research team using the SAE form within the REDCap trial database as soon as they are aware of the event. The central trial team is automatically notified of the SAE report through the database. If the electronic system on REDCap fails, sites will be asked to print out the SAE CRF from the PDF version contained in their Electronic Investigator Site File (eISF). They will use this hard copy to complete the event details using wet-ink and then scan and send a copy to the central team via email.

